1 2

3

# 17 **SYNOPSIS**

Sponsor	Guangzhou Magpie Pharmaceuticals Co., Ltd.
Investigational Product	TBN Tablets
Name of Active Ingredient	TBN
Study Title	A multi-center, randomized, double-blind, placebo-controlled study evaluating the efficacy and safety of tetramethylpyrazine nitrone (TBN) tablets for treatment of amyotrophic lateral sclerosis (ALS)
Study Objectives	To evaluate the efficacy and safety of TBN tablets in patients with ALS, and to explore the optimal effective dose.
Clinical Phase	Phase 2
Study Duration	Treatment period: 180 days
	This study is a randomized, double-blind, placebo-controlled parallel study. Patients with ALS will be enrolled. After screening for inclusion and exclusion criteria, subjects are to be randomized to receive either TBN or placebo.  Treatment group 1: TBN tablets 600 mg group (TBN 300 mg × 2 tablets + placebo 300 mg × 2 tablets are taken orally twice daily, TBN 100 mg ×
Study Design	6 tablets + placebo 100 mg × 6 tablets instead if the subjects are not able to take 300 mg tablets because of disease progression).
	Treatment group 2: TBN tablets 1200 mg group (TBN 300 mg $\times$ 4 tablets are taken orally twice daily, TBN 100 mg $\times$ 12 tablets instead if the subjects are not able to take 300 mg tablets because of disease progression).
	Placebo group: placebo group (placebo 300 mg $\times$ 4 tablets are taken orally twice daily, placebo 100 mg $\times$ 12 tablets instead if the subjects are not able to take 300 mg tablets because of disease progression).

	Screening period: 3 months.						
Visit Plan	The eligible subjects will be randomized, with no administration on the day of randomization and the first administration on the next day (Day 1). Clinic visits will occur at the end of Month 1, Month 3, and Month 6 (or withdrawal) for safety- and efficacy-related examinations. Phone calls will be conducted at Day 7, the end of Month 2, Month 4, and Month 5, and the 2nd week after the last dosing.						
Planned Enrollment Number of Patients	Number of patients to be enrolled: 150, all of whom are to be randomized to 2 treatment groups and 1 placebo group, 50 patients per group, respectively.						
Study Population	Patients with mild to moderate ALS						
	Subjects will be enrolled in this trial only if they meet all the following criteria:						
	1) Male or female, aged 45 to 70 years old (including 45 and 70 years old);						
	2) Subjects diagnosed with clinically definite or clinically probable ALS according to revised El Escorial criteria-1998 by the World Federation of Neurology;						
	3) Subjects of $\leq 2$ years after the onset of ALS before randomization;						
Inclusion Criteria	4) The ALSFRS-R scores are all ≥ 2 points, and the respiratory function is 4 points before randomization;						
	5) ALSFRS-R has a decrease of 1-4 points during a 3-month screening period;						
	6) Forced Vital Capacity (%FVC) ≥ 80% before randomization;						
	7) Understand and comply with the study rules, voluntarily participate, and sign an informed consent form (informed consent form is voluntarily signed by the subject himself/herself or his/her legal representative).						
	Subjects who meet one of the following conditions will not be eligible for this trial:						
Exclusion Criteria	1) Familial ALS (judge by family history);						
	2) Those with obvious cognitive impairment (MMSE scale: illiterate group ≤ 19 points, primary school group ≤ 22 points, junior high						

school and above group ( $\geq 8$  years of education)  $\leq 26$  points;

- 3) Obvious dysphagia;
- 4) Severe renal insufficiency: creatinine clearance < 30 mL / min (Cockcroft-Gault formula), or other known severe renal insufficiency disease;
- 5) Severe liver damage: ALT, AST > 3 times the upper limit of normal level, or other known liver diseases such as acute and chronic hepatitis, cirrhosis, etc.;
- 6) Acute myocardial infarction or interventional therapy in the past 6 months, heart failure patients (in accordance with NYHA classification III-IV patients) at the screening period;
- 7) Combined with malignant tumors and serious diseases of blood, digestion or the other systems;
- 8) Allergic to Investigational Product (IMP) or tetramethylpyrazine;
- 9) Female patients during pregnancy and lactation;
- 10) Participate in other clinical studies within 30 days before screening, or is participating in other clinical studies;
- 11) Other circumstances that the investigator considered unsuitable for participation in the study.

# Investigational medicinal product

TBN tablets, strengths: 100 mg / tablet and 300 mg / tablet, provided by Guangzhou Magpie Pharmaceuticals Co., Ltd.

Placebo tablets, strengths: 100 mg / tablet and 300 mg / tablet, provided by Guangzhou Magpie Pharmaceuticals Co., Ltd.

# Efficacy

**Endpoints** 

### **Primary Endpoint:**

✓ Difference between the groups in the ALSFRS-R scores change from baseline at Day 180;

# **Secondary Endpoints:**

✓ Difference between the groups in the proportion of events such as death, tracheotomy, invasive ventilation, or continuous non-invasive ventilation ( $\geq 22$  h per day for  $\geq 10$  days);

	✓ Difference between the groups in gripe strength change from baseline at Day 180;
	✓ Difference between the groups in respiratory function (%FVC) change from baseline at day 180;
	✓ Difference between the groups in ALSAQ-40 scores change from baseline at Day 180.
	Safety evaluation including: adverse events (AEs), serious adverse events (SAEs), clinical laboratory tests (hematology, urinalysis, blood biochemistry, thyroid function), vital signs (blood pressure, respiratory rate, pulse and body temperature), 12-lead electrocardiogram (ECG) examination, physical examination.
	Primary safety indicators:
Safety Assessment Indicators	Percentage of subjects with serious adverse reactions within 180 days; (Adverse reactions: AEs related to the IMP)
	Secondary safety indicators:
	Percentage of subjects with adverse reactions within 180 days;
	AEs, SAEs, and their incidence, the clinical manifestations, severity, time of occurrence, end time, duration, treatment measures and outcomes of these are to be recorded, and the correlation between AE and IMP are to be determined.
PK/PD and Biomarkers	The cerebrospinal fluid (Tmax after administration, optional) is to be taken (in part of subjects) at baseline period before administration and 180 days after administration, and the concentration of TBN and its metabolites in cerebrospinal fluid and plasm are to be measured for PK/PD analysis. Biomarkers, such as 3-NT, 8-OHdG, NFL levels in cerebrospinal fluid are to be determined.
Treatment	Subjects need to terminate the treatment permanently if the following events occur:
Termination Termination	✓ The subject is pregnant;
	✓ The subject withdraws informed consent;
	✓ The subject has a medical emergency that requires to terminate the

	treatment permanantly, such as death, tracheotomy, invasive ventilator assisted ventilation, or continuous non-invasive ventilator assisted ventilation (≥ 22 h per day for ≥10 days);  ✓ The subject has a medical emergency requiring a unblinding of the treatment of the subject;  ✓ Determinations based on medical reasons made by investigator.
Combined Medication and Treatment	
 
✓ Except edaravone, all other drugs are not prohibited.
 
✓ Riluzole administration is permitted during the study, but is regulated under the guidance of the investigator.
 
✓ All concomitant medications other than the IMP within 180 days should be recorded and counted for the impact on the subject's outcome;
 
✓ All non-medicine therapies need to be recorded in the medical records.
 

Estimating Sample Size	This trial is an exploratory study in safety and efficacy. No statistical assumptions will be made, and statistics will not calculate the sample size.

# 8 TRIAL SCHEDULE

	Time		eening riod*	Baseline#	Day	Day	Day		Day	Day	Day	End- of-stu	
Items		First	Second	Day 0	7 T	30 ±	60 ±3 T	90 ± 7		150 ±3 T	180 ± 7	dy visit T	Withdrawal &
Informed cons	sent	X											
Review of criteria	inclusion and exclusion	X		X									
Subject	Medical history/allergic history	X											
characteristi	Demographics	X											
cs	Height	X											
	Weight	X		X		X	$X^{^{Y}}$	X	$X^{^{Y}}$	$X^{^{Y}}$	X		X
	ALSFRS-R	X	X	X		X		X			X		X
	ALSAQ-40			X							X		X
Efficacy evaluation	Grip strength test 	X		X		X		X			X		X
	Respiratory Function (%FVC)	X		X		X		X			X		X
Safety evaluation	Vital signs (blood pressure, respiratory rate, pulse, temperature)	X		X		X	$X^{^{Y}}$	X	$X^{^{Y}}$	$X^{^{Y}}$	X		X
	Physical examination	X		X		X	$\mathbf{X}^{^{\mathrm{Y}}}$	X	$X^{^{Y}}$	$\mathbf{X}^{\mathrm{Y}}$	X		X

	12-lead ECG	X		X		X		X			X		X
	Hematology, urinalysis, chemistry 	X		X		X		X			X		X
	Thyroid function 			X		X		X			X		X
MMSE scale 		X											
Urine pregna	-	X		X		X		X			X		X
Cerebrospina	l fluid sampling 			X							X		
Blood sampli	ng for drug concentration 										X		
Assigning ran	Assigning randomization numbers			X									
Dispensing IMP				X		X	X	X	X	X			
Drug accountability/return, diary card return						X	X	X	X	X	X		X
Drug adminis	tration				X	X	X	X	X	X	X		
Concomitant treatment (medication & non-medication)		X	X	X	X	X	X	X	X	X	X	X	X
Safety evaluation	Monitoring and recording AEs		X	X	X	X	X	X	X	X	X	X	X
	Monitoring and recording SAEs		X	X	X	X	X	X	X	X	X	X	X

21

22

23

24

**Note:**\* Screening period: Perform ALSFRS-R examinations twice to confirm subjects meeting the inclusion criteria; the two ALSFRS-R examinations will be performed with  $90 \pm 3$  days interval. For subjects having an ALSFRS-R scores within the previous 3 months with appropriate documentation (such as medical record), the results of the previous examination can be used as the first ALSFRS-R result for the screening period, at the discretion of the investigator.

[figure not shown]
# Baseline: Subjects enter baseline period after screening successfully. The examination cannot be repeated if the same examinations are performed at

- baseline and screening with the results within 7 days. Randomization is performed after eligibility for the baseline assessment, with no administration on
- 26 the day of randomization and the first administration on the next day (Day 1).
- Withdrawal: Only for subjects dropping out of the study, withdrawal visits from 7 days to 14 days after the last dose.
- T Visiting by phone: Subjects are encouraged to visit the hospital for follow-up at Day 60, Day 120, and Day 150; If the subject cannot visit due to
- medical reasons, phone visits can be accepted for the subject, but the family member need to visit the hospital at the specified visit to get the new
- medication and diary card, as well as to retrieve the left-over medication and the diary card recording the medication taken; the end-of-study visit is at the
- 31 2nd week after the end of the study.
- 32 Y Perform when the subject arrives at the hospital to collect the new medication and diary card in person, but not if the family member delegating visit.
- 33 1. Grip strength measurement: Measure the subject's maximum grip strength (using an electronic grip strength meter).
- Hematology, urinalysis, chemistry: On the day of testing, subjects attend the study site fasting for blood collection and testing; Hematology includes
- 35 white blood cell count, red blood cell count, platelet count, hemoglobin, neutrophil percentage, and lymphocyte percentage. Chemistry includes ALT
- AST, TBIL (Total bilirubin), Cr (Serum creatinine), BUN (Blood Urea Nitrogen), CK (Creatine Kinase);
- 37 3. Thyroid function includes free triiodothyronine (FT3), free thyroxine (FT4), thyroid stimulating hormone (TSH);
- 38 4. Subjects with significant cognitive impairment (MMSE score: illiterate group ≤ 19, primary school group ≤ 22, middle school group and above (>8
- years of schooling)  $\leq 26$ ;
- 40 5. Cerebrospinal fluid (CSF) collection: For subjects agreeing cerebrospinal fluid collection for drug concentration and biomarker levels, 4 mL of CSF
- 41 is collected at baseline and  $180 \pm 3$  days after treatment (3 h  $\pm$  30 min after the first dose on the same day), and the levels of TBN and its metabolite,
- 42 5-OH-TBN, are determined in the CSF of less than 10 subjects in each group at 180 ± 3 days after treatment; The levels of 3-NT, 8-OHdG, and NFL
- 43 (Neurofilament light chain) in the CSF of all subjects agreeing CSF collection at baseline and at  $180 \pm 3$  days after treatment are determined. The sample
- 44 is not collected at  $180 \pm 3$  days after treatment for the subject without baseline sampling.
- 45 6. Blood sampling for drug concentration: Blood sample is collected before the first dose and at 3h±30 min after the first dose on 180±3 day (the same
- day) after administration, 4 mL each time, and plasma levels of TBN and its metabolite 5-OH-TBN are determined.

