#### Safety and Efficacy

- 417 TBN is a new chemical drug, whose single-ascending-doses study (SAD) and
- 418 multiple-ascending-doses study (MAD) has been completed. The summary table of adverse
- reaction information can be found in section 5 of the investigator's brochure.

- 420 In the SAD and MAD study, TBN was well tolerated in all subjects without SAE observed, and
- 421 no AEs leading to early withdrawal from the trial and AEs leading to drug or non-drug
- intervention in this study.
- During the study, 52 subjects were enrolled and all of the subjects were capable of compliance
- 424 the protocol. A total of 3 drug-related AEs occurred in 2 subjects (3.85%), among which 1
- subject in the 1200 mg single dose group had a decrease in the percentage of neutrophils (1.9%),
- and this subject had a drug eruption after multiple administration of 1200 mg (1.9%). One
- subject in the 1200 mg food-affected group was found elevated alanine aminotransferase (1.9%).
- The above adverse reactions were of grade 1 in CTCAE and recovered to normal without any
- 429 medical intervention. No adverse reactions were observed in 400 mg, 600 mg and 1800 mg
- 430 groups.
- In this study, a total of 23 AEs occurred in 18 subjects, which were determined by the
- investigator to be unrelated to the IMP. Among the above AEs, the incidence of elevated white
- blood cell count was 7.7% (4 cases), increased oral ulcer was 5.8% (3 cases), elevated
- neutrophilic granulocyte count was 3.8% (2 cases), and increased platelet count, positive urine
- white blood cell count, and elevated creatinine phosphokinase in blood was 1.9% (1 case),
- 436 respectively. All of the above AEs were of CTCAE grade 1 severity and disappeared
- 437 spontaneously without any treatment.
- 438 Other safety indicators, including vital signs, physical examination and electrocardiogram
- 439 examination, no abnormal results of clinical significance at baseline and each visit were
- 440 observed.
- TBN for injection is used for the treatment of acute ischemic stroke. The phase I clinical trial has
- been completed and the phase II clinical trial is ongoing. The safety information of the phase I
- clinical study of TBN for injection is as follows:
- In the single-dose safety, tolerability and pharmacokinetics study of TBN for Injection, a total of
- 445 68 subjects were enrolled, 52 subjects in the TBN for Injection group and 16 subjects in the

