- placebo group. No AEs, SAEs and toxic reactions were observed. There were 10 adverse
- reactions in 3 subjects (37.5%) in the 400 mg group, 3 adverse reactions in 3 subjects (37.5%) in

449

450

451

452

453

454

455

456

457

458

459

460

461

462

463

464

465

466

467

468

469

470

471

472

473

474

475

476

the 700 mg group, 6 adverse reactions in 2 subjects (25.0%) in the 1000 mg group, and there were no adverse reactions of the other groups. The highest incidence of adverse reactions was decreased white blood cell count and decreased neutrophil count, both in 3 cases (4.4%), followed by decreased haemoglobin, increased blood lactate dehydrogenase, and decreased neutrophil percentage, both in 2 cases (2.9%). The overall severity of adverse reactions was grade 1 in 7 subjects (10.3%), grade 2 in 3 subjects (4.4%) with decreased neutrophil counts (400 and 1000 mg groups), and grade 3 in 1 subject (1.5%) with decreased neutrophil counts (1000 mg group). Safety analyses including laboratory parameters, vital signs, physical examination, electrocardiogram, neurological and behavioral tests, did not change significantly from baseline at each post-baseline visit for each dose group.

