A total of 128 healthy subjects in completed clinical trials received TBN, including TBN tablets and TBN for injection. The safety and tolerability evaluation included vital signs, physical examination, ECG, and laboratory test. All AEs were recorded. The TBN was safe, with no SAEs, AEs leading to withdrawal from the study, or AEs leading to death or dose-limiting toxicity occurred during the study. Summarized safety for TBN administered orally and intravenously in healthy subjects, drug-related safety information is as follows: The adverse reactions in the single-dose, multiple-dose and food effect study in healthy Chinese human subjects receiving TBN tablets orally included a decreased percentage of neutrophils (1.9%), eruption (1.9%),and increased alanine aminotransferase (1.9%).single-ascending-dose study of healthy subjects receiving TBN for injection intravenously, the adverse reactions included decreased white blood cell count (4.4%), decreased neutrophil count (4.4%), decreased hemoglobin (2.9%), increased blood lactate dehydrogenase (2.9%), decreased percentage of neutrophils (2.9%), decreased hematocrit (1.5%), positive Coombs test (1.5%), decreased mean cellular hemoglobin (1.5%), decreased mean cellular hemoglobin concentration (1.5%). In the multiple-ascending-dose study of healthy subjects receiving TBN for Injection

- intravenously, adverse reactions included increased gamma-glutamyl transferase (4.2%),
- decreased erythrocyte count (4.2%), decreased hemoglobin (4.2%), and decreased erythrocyte
- pressure volume (4.2%).

510

531

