# 1412 8.3.4 Analysis of Secondary Efficacy Endpoint

- 1413 The following four secondary efficacy endpoints, the continuous data of each visit in different
- groups will be described using mean  $\pm$  standard deviation and median (minimum, maximum).
- 1415 Comparing with the baseline data, the paired T test is to be used to compare the within-group
- before-after differences. Analysis of variance (ANOVA) is to be used before and after treatment
- between groups. For the first secondary endpoint (endpoint event and disease exacerbation
- event), Kaplan-Meier plots will be used to describe the survival rate of patients without endpoint
- event, and Log-Rank test or non-parametric statistical method is to be used to compare the
- indicators of each group.
- 1421 (1) Proportion of endpoint events, including death, tracheotomy, invasive ventilator-assisted
- ventilation, or continuous non-invasive ventilator-assisted ventilation ( $\geq$  22 h per day for  $\geq$
- 1423 10 days);
- 1424 (2) Difference between the groups in grip strength change from baseline at Day 180;
- 1425 (3) Difference between the groups in respiratory function (%FVC) change from baseline at
- 1426 Day 180;
- 1427 (4) Difference between the groups in ALSAQ-40 scores change from baseline at Day 180.
- 1428 **8.3.5 Safety Assessment**
- Descriptive statistical analysis is mainly to be used to list the AE and SAE, drug-related AE and
- SAE that occurs in this trial, and between-group comparisons are conducted using the  $X^2$  test or
- 1431 Fisher's test.
- 1432 Descriptive statistics are to be used to summarize laboratory tests, vital signs, and
- electrocardiograms, etc. Shift tables are to be used to describe changes in normal/abnormal
- results before and after administration, such as laboratory tests, electrocardiograms, and physical
- 1435 examinations.
- 1436 **8.3.6 Interim Analysis**
- 1437 Not Applicable

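### Haematology note 2 names neutrophils only as a percentage; naming the absolute count, recoverable from the same panel, would give better safety tables at no cost

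*Protocol*

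**What the plan says.** Note 2 to the Trial Schedule says that haematology includes "white blood cell count, red blood cell count, platelet count, hemoglobin, neutrophil percentage, and lymphocyte percentage". White cells, red cells and platelets are counts. Neutrophils and lymphocytes are percentages. The protocol mentions no derived neutrophil count.

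The earlier human data are in Section 1.2.4, Safety and Efficacy. In the single-dose study of TBN for injection, "68 subjects were enrolled, 52 subjects in the TBN for Injection group and 16 subjects in the" placebo group. Decreased white cell count and decreased neutrophil count were the most frequent reactions, with 3 cases each. On severity the section reports "grade 2 in 3 subjects (4.4%) with decreased neutrophil counts" and "grade 3 in 1 subject (1.5%) with decreased neutrophil counts". Section 1.3.1 lists decreased neutrophil count (4.4%) and decreased neutrophil percentage (2.9%) as separate reactions in that study.

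For the tablets, the formulation used in this trial, Section 1.2.4 reports one neutrophil reaction among 52 subjects. It was a decreased percentage after a single 1200 mg dose. All tablet reactions were grade 1.

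Section 8.3.5 states: "Descriptive statistics are to be used to summarize laboratory tests, vital signs, and" electrocardiograms. It adds shift tables of normal against abnormal results before and after administration. Sections 6.1.4 and 6.2.2 require grading by CTCAE 5.0.

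**The concern.** The variable named for neutrophils is not the one in which TBN has shown its most severe laboratory reactions. The protocol's own risk summary does not treat count and percentage as interchangeable.

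A percentage is relative to the white cell total. If all white cells fall together, the percentage does not move. That pattern is plausible, because white cell count and neutrophil count were each reduced in 3 cases. If another cell type rises, the percentage can fall while the neutrophil count stays normal.

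Shift tables by arm built on the percentage could therefore put some subjects with a low count in the normal column, and some with a normal count in the abnormal column. The trial is exploratory, is meant to support a phase 3 study and doses for about 180 days. It should show a haematological effect in the clearest variable it has.

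**Working it through.** **1. The protocol's own figures.** 3/68 = 4.4% and 1/68 = 1.5%, so the injection percentages reproduce on all 68 enrolled, placebo included. On the 52 who received TBN, 3 cases would be 3/52 = 5.8%. The tablet figure is 1/52 = 1.9%. The text gives 3 cases of decreased neutrophil count but 3 subjects at grade 2 plus 1 at grade 3. These agree only if one subject is counted at both grades.

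**2. Identity.** Absolute neutrophil count = WBC × neutrophil percentage / 100 (units 10⁹/L). Both factors are in note 2.

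**3. Illustrative records.** The values are mine, and the lower limits are assumptions: count 1.8, WBC 3.5, percentage 40%.

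| WBC | Neutrophil % | Count | Percentage reads | WBC reads |
|---|---|---|---|---|
| 2.2 | 55 | 2.2 × 0.55 = 1.21 (low) | normal | low |
| 8.5 | 38 | 8.5 × 0.38 = 3.23 (normal) | low | normal |
| 3.7 | 43 | 3.7 × 0.43 = 1.59 (low) | normal | normal |

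The first record is caught by WBC. The third is low only because the assumed count limit is 1.8; at a limit of 1.5 it is normal.

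**4. How far WBC and percentage cover for each other.** If both are at or above their lower limits, the smallest possible count is the product of the limits:

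- 3.5 × 0.40 = 1.40
- 4.0 × 0.40 = 1.60
- 3.5 × 0.50 = 1.75
- 4.0 × 0.50 = 2.00

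Under any of these pairs, a count below 1.0 always makes at least one of the two abnormal.

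**5. Simulation.** Nothing in this step comes from the protocol except the choice of variables. Baseline WBC is lognormal with mean 6.0 and SD 1.5. Neutrophil percentage is normal with mean 58 and SD 8. The correlation is 0 or 0.4, with 2,000,000 subjects per scenario. In scenario A all white cells fall by 40%, so the percentage is unchanged. In scenario B neutrophils alone fall by 40%, so the percentage (as a fraction p) becomes 0.6p/(1 − 0.4p). For an average subject the count falls from 6.0 × 0.58 = 3.48 to 2.09 in both. The percentage stays at 58% in A and becomes 0.348/0.768 = 45% in B.

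Results at limits of 1.8 (count), 3.5 (WBC) and 40% (percentage):

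| Quantity | A: all white cells | B: neutrophils only |
|---|---|---|
| Low counts with normal percentage | 97% | 46–56% |
| Low counts missed by both percentage and WBC | 5–7% | 23–24% |
| Normal counts flagged low on percentage | under 1% | 9–15% |

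**6. Sensitivity of the miss on both, scenario B.**

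- Count limit 1.5: about 3%.
- Count limit 2.0: 35–37%.
- Count limit 1.8 with a WBC limit of 4.0: about 6%.
- Count limit 1.8 with a percentage limit of 50%: about 0.2%.
- Counts below 1.0: 0% in every combination tried.

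**The case against.** The strongest reply is that nothing is missing from the data. The list in note 2 opens with the white cell count from the same sample, so the neutrophil count can be derived exactly for every subject and visit. Deriving a variable is ordinary SAP work, and Section 8 leaves detail to a SAP that is not shown. Note 2 says what haematology includes, which does not make the list exhaustive. This stands, and it limits the point to which variable the protocol names.

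A reader might infer that a neutrophil effect could never be tabulated by arm. The documents do not support that. Both factors of the count are collected. Under Section 6.1.1 a clinically significant laboratory abnormality is an adverse event. Such events are graded by CTCAE 5.0, described by treatment group (Section 6.1.3) and compared between groups (Section 8.3.5).

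A reader might also take the 97% as the share of low counts that would go unseen. It is the share with a normal percentage taken alone. Once WBC is read as well, it drops to 5–7%.

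Finally, the grade 2–3 reactions came from single doses of the injection. They cannot be presented as a tablet signal: the one tablet reaction was a grade 1 change in the percentage, the variable that note 2 does list. This also stands. It does not make the percentage the better variable, because the active ingredient is the same and exposure here is far longer than the 7 days of continuous tablet dosing cited in Section 1.2.4.

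**Conclusion.** The point holds as a low-priority improvement in the choice of tabulated variable. The protocol names the percentage, while its own injection data place the grade 2–3 reactions in the count and its risk summary keeps the two apart. It is not an error that loses data, and it does not show that neutropenia would go unreported.

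That the percentage alone can mislead in both directions is arithmetic and needs no assumption beyond a reference limit. How often WBC and percentage together would miss a low count depends wholly on assumed distributions and limits. At a 40% fall it is 5–7% if all white cells fall and 23–24% if neutrophils alone fall, at the limits in step 5. For count limits of 1.5 to 2.0 the neutrophil-only figure runs from about 3% to 37%. Deep falls, below 1.0, are not missed. What could be blurred is a mild to moderate shift by arm.

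**What to change.** In note 2 of the Trial Schedule, add the absolute neutrophil count, either as reported by the laboratory or derived as WBC × neutrophil percentage / 100, at every haematology visit. In Section 8.3.5, name it as the neutrophil variable for the by-visit summaries, the CTCAE grading of laboratory values and the shift tables, with the percentage kept as supportive. While editing, clarify in Section 1.2.4 whether one subject is counted at both grade 2 and grade 3.

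The cost is one derived variable in the database and one line in each of the two places. No extra blood, visit or assay is needed.

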In the multiple-dose safety, tolerability and pharmacokinetics study of TBN for Injection, a total of 24 subjects were enrolled. Among the 24 subjects, 3 (12.5%) were observed to have 6 AEs, all of which were treatment emergent adverse events (TEAE). The incidences of TEAEs in each group were as follows: 1 subject (8.3%) in the 700 mg group had 2 AEs, and 2 subjects (16.7%) in the 1400 mg group had 4 AEs. No SAEs, AEs leading to withdrawal from the study, or AEs leading to death or dose-limiting toxicity occurred during the study. No significant effects on the safety indicators, such as laboratory tests, vital signs, physical examination, electrocardiogram data, and nervous system and behavioral examination, were observed. Studies showed that TBN and 5-OH-TBN had the best protective effect on cerebral cortical neurons at the concentrations of 30  $\mu$ M $\sim$ 300  $\mu$ M (P < 0.01, compared with the control group) in vitro, followed by 10  $\mu$ M (P< 0.05, compared with the control group). After 7 days of continuous administration of TBN tablets, the  $C_{max}$  of TBN in 600 mg and 1200 mg groups were 43  $\mu$ M and 114  $\mu$ M, respectively; the Cmax of 5-OH-TBN was 51 µM and 111 µM, respectively. The concentration of TBN and 5-OH in the two dose groups can reach the range of effective drug protection concentrations in vitro. In 600 mg and 1200 mg groups, the prototype of TBN and 5-OH-TBN are both higher than 30 µM, which can reach the minimum effective protective concentration of drug in vitro and should display a good neuroprotective effect.

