#### 1.3. Summarized Risk-benefit Assessment

#### 1.3.1. Known Potential Risks

478

479

480

481

482

483

484

485

486

487

488

489

490

491

492

493

494

495

496

497

498

499

500

501

502

503

504

505

506

In a non-clinical study in SD rats, after 4 consecutive weeks of treatment with TBN for injection, the main adverse reactions observed were slow weight gain, decreased food consumption, decreased animal activity, and the emergence of tachypnea and spasm. The main adverse reactions in beagles, by contrast, were increased muscle tone, decreased food consumption, unstable gait, decreased motor activity, prone and motionless stance, curling up and decreased movement in behavior, loose stools, drooling and decreased thymic weight. Symptoms of toxicity were apparent primarily in the nervous system in the form of altered behavioral activities. With the exception of slow weight gain and decreased food intake, the other toxic effects, such as decreased activity, tachypnea and twitching, were short-lived. No clinical abnormalities were observed during the recovery period. In rats administered for a prolonged period of 26 weeks, a decrease in the weight of the thyroid and parathyroid glands was observed in the ≥50 mg/kg dose group, and diffuse follicular atrophy of the thyroid gland was observed in the ≥50 mg/kg dose group. In beagle dogs administered for a prolonged period of 39 weeks, an increase in alkaline phosphatase was observed in the blood of the males in the 100 mg/kg and 200 mg/kg dose groups.

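### The only listed chemistry panel leaves out alkaline phosphatase and gamma-glutamyl transferase, two of the three liver-enzyme signals in the protocol's own risk section, so scheduled visits do not systematically assess them.

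*Protocol*

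**What the plan says.** **The panel.** Note 2 to the Trial Schedule reads "Chemistry includes ALT" and continues with AST and then "TBIL (Total bilirubin), Cr (Serum creatinine), BUN (Blood Urea Nitrogen), CK (Creatine Kinase"). That makes six analytes. The Synopsis and sections 3.3.2, 3.5 and 3.6 speak only of blood biochemistry and list no analytes.

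**When it is run.** The Trial Schedule marks chemistry in six columns: first screening, baseline, Day 30, Day 90, Day 180 and withdrawal.

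**The signals.** Section 1.3.1 (Known Potential Risks) reports for the 39-week dog study that "an increase in alkaline phosphatase was observed in the blood of the males in the 100 mg/kg and 200 mg/kg dose groups". For the multiple-ascending-dose study of the intravenous form it says "adverse reactions included increased gamma-glutamyl transferase (4.2"%). For the tablets it lists "increased alanine aminotransferase (1.9"%). Section 1.2.4 gives the detail of that last case: one "subject in the 1200 mg food-affected group was found elevated alanine aminotransferase (1.9"%).

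**How the results are used.** Section 8.3.5 plans descriptive summaries of laboratory tests and shift tables between normal and abnormal.

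**The concern.** A phase 2 trial that sets out to explore safety and to support phase 3 (section 3.1.4) would be expected to measure, at its scheduled visits, the laboratory changes that its own risk section names. Here the list of analytes and the list of signals do not match. Two named enzymes have no scheduled test.

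The length of treatment makes this more relevant. Section 1.2.4 describes repeat tablet dosing of 6.5 to 7 days in healthy volunteers, whereas this trial doses patients for 180 days. The ALP rise was reported under prolonged dosing, which this trial introduces in humans with the tablets.

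If the panel is followed as listed, the final report can make no between-arm statement on ALP or GGT. A statistical analysis plan cannot repair that, because it can only analyse what was collected.

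**Working it through.** **1. Reproduce the protocol's own incidences.**
- GGT: in the multiple-dose intravenous study a total "of 24 subjects were enrolled" (section 1.2.4). 1/24 = 4.17%, which rounds to the stated 4.2%. The figure is one subject.
- ALT: 52 subjects were enrolled in the tablet studies. 1/52 = 1.92%, which rounds to the stated 1.9%. The figure is one subject.
- ALP: no incidence is given for the dogs, so nothing can be computed.

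**2. Set the signals against the panel.**

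| Signal in section 1.3.1 | Source | On the panel in note 2? |
|---|---|---|
| ALT raised | Human, tablets, 1/52 | Yes |
| GGT raised | Human, intravenous, repeated doses, 1/24 | No |
| ALP raised | Male dogs, 100 and 200 mg/kg, 39 weeks | No |

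Two of the three named liver-enzyme signals are unlisted.

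**3. Count the chemistry points.** Six columns are scheduled. None is stated to carry ALP or GGT. A subject who completes the trial passes at most five of them, because the withdrawal column applies only to drop-outs.

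**4. Compare durations.** Treatment here is 180 days. The dog study ran 39 × 7 = 273 days. Repeat tablet dosing in humans was about 7 days, so exposure rises by a factor of about 180/7 = 26. The protocol does not say when the ALP rise appeared in the dogs.

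**5. Compare doses, as far as the document allows.** The high-dose arm takes 1200 mg twice daily, 2400 mg per day. Body weight is not given. At an assumed 50 to 80 kg:
- 2400/50 = 48 mg/kg/day and 2400/80 = 30 mg/kg/day
- 100/48 = 2.1 and 100/30 = 3.3

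The lowest dog dose with an ALP rise is thus about 2.1 to 3.3 times the high-dose arm on plain mg/kg, reading the dog dose as a daily dose. Dog exposures are not given, so this ratio is not a safety margin.

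**6. What measuring GGT could yield.** Assume the true incidence in this trial is the 1/24 seen with the intravenous form in healthy subjects. Then P(at least one case) = 1 − (23/24)^n:
- one TBN arm, n = 50: 0.881
- both TBN arms, n = 100: 0.986

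One case in 24 fixes the rate poorly. Its exact 95% confidence interval is 0.1% to 21.1%. Over that range the probability runs from 0.051 to above 0.999 with n = 50, and from 0.100 to above 0.999 with n = 100. The trial is large enough to learn something if the rate is near the one observed. It may see nothing if the rate is at the low end.

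**The case against.** The other side has several fair points.

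- **The signal seen with the trial's own product is covered.** ALT is the only liver-enzyme reaction listed for the tablets, and ALT, AST and total bilirubin are on the panel at every chemistry point. This stands. A reader might infer that ALP and GGT are the only liver signals named, or that liver monitoring is absent. Neither is so.
- **The list is not expressly closed.** Note 2 says that chemistry includes these tests, and a site could run more. This stands as to wording but does not cure the gap. If some sites measured ALP and GGT and others did not, the shift tables could not compare the arms on them.
- **There are other routes to detection.** Section 3.5.3.1 lets the investigator add visits, and section 6.1.1 makes any clinically significant abnormality an adverse event. A reader might therefore go too far in saying that the trial cannot detect a rise, or that one would stay hidden until bilirubin rose. ALT or AST could rise too, and an unscheduled test could find it. But extra visits depend on the patient's condition, and an enzyme rise without symptoms would not prompt one.
- **The evidence is thin.** GGT rests on one subject given a different formulation by a different route, and section 1.2.4 reports no significant effect on laboratory tests in that study. Section 1.3.1 gives the dog finding in one sentence, without size, reversibility or tissue of origin. This stands. A reader might infer a cholestatic pattern, or that ALP was the sole finding in the dogs. The protocol describes no such pattern, and the full dog study is not shown.
- **Panel breadth is a sponsor's judgement.** True in general. Here, though, the sponsor's own text lists the GGT rise among drug-related adverse reactions, and the protocol gives no reason for leaving it untested.

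**Conclusion.** The point holds as a gap in systematic safety assessment. Two of the three liver-enzyme signals named in section 1.3.1 are missing from the only chemistry list, at all six scheduled points, in a trial that extends repeat tablet dosing from about 7 to 180 days.

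It does not show that TBN harms the liver or that liver monitoring is lacking. It changes no sample size, power or error rate, and no efficacy endpoint depends on it. The size of the risk cannot be judged from the document: the dose comparison rests on assumed body weights without dog exposures, and the detection probabilities rest on carrying an intravenous healthy-volunteer rate over to oral dosing in ALS.

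The case for change is therefore modest evidence of risk set against a very small cost of measuring it.

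**What to change.** In note 2 of the Trial Schedule, add ALP and GGT to the chemistry list, so that both are measured at first screening, baseline, Day 30, Day 90, Day 180 and withdrawal from the serum already drawn. State in section 8.3.5 that both enter the laboratory summaries and shift tables.

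The cost is two more assays per sample, the matching eCRF fields, a minor amendment, and a few more incidental out-of-range values to review. No visit or blood draw is added. Lactate dehydrogenase and hematocrit, also named in section 1.3.1, could be added in the same step, but that is optional and not part of this point.
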